8.1 Definitions

8.1.1 Adverse event

An **adverse event** is “any unfavourable and unintended sign, symptom or illness that develops or worsens during the period of observation in the Register. This definition does not imply that there is a relationship between the adverse event and the device under investigation.” [21]

Surgical procedures themselves are not adverse events; they are therapeutic measures for conditions that require surgery. The condition for which the surgery is required is an adverse event, if it occurs or is detected during the Register follow-up period.

A **serious adverse event** is an adverse event which

- a) led to a death
- b) led to a serious deterioration in the health of a subject that
 1. resulted in a life-threatening illness or injury
 2. resulted in a permanent impairment of a body structure or a body function
 3. required in-patient hospitalization or prolongation of existing hospitalisation
 4. resulted in medical or surgical intervention to prevent permanent impairment to body structure or a body function
- c) led to foetal distress, foetal death or a congenital abnormality or birth defect

8.1.2 Adverse device effect

An **adverse device effect** is “any untoward and unintended response to a medical device (this definition includes any event resulting from insufficiencies or inadequacies in the instructions for use or the deployment of the device. This definition includes any event that is a result of a user error)”. [21]

A **serious adverse device effect** is “an adverse device effect that has resulted in any of the consequences characteristic of a serious adverse event or that might have led to any of these consequences if suitable action had not been taken or intervention had not been made or if circumstances had been less opportune”

8.2 Documentation and reporting of adverse event by the investigator

All subjects who have adverse events, whether considered associated with the use of the implant or not, must be monitored to determine the outcome.

The assessment of the causal relationship between the adverse event and the device will be reported by the surgeon as:

- definitively
- probably
- possibly
- probably not
- definitively not

All serious adverse events, serious adverse device effect, adverse device effects and unexpected adverse events, in accordance with the above definitions, must be reported to the sponsor **within 24 hours** from their occurrence, using the *adverse event report form*. Written and detailed subsequent follow-up reports will be provided to the sponsor.

A Serious Adverse Event report form should be completed by the investigator and sent by email ([contact]) to the sponsor, **within 24 hours**. If at the time of sending the report, all details are not available by the investigator; this one must send it with the available data and then seek to obtain complementary information. The complementary information will be sent by the investigator to the sponsor as soon as it will be available.

Please contact your local Stryker Clinical contact, or the study manager for any adverse events.

In addition, all adverse events, serious or not, occurring between two planned visits will be reported in the CRF.

Death will be both reported in the *serious adverse event report form* and in the *termination form* part of the CRF.

Moreover the investigator should send to the Sponsor a copy of the imaging exam when performed at the time of the adverse event.

The investigator will evaluate the adverse event and determine the most appropriate actions.

The sponsor will report to Competent Authorities and Ethic Committees adverse events occurred during the study in accordance with applicable regulations.

9 PATIENT WITHDRAWALS

Patients are free to withdraw from the Surveillance at any time and are under no obligation to provide a reason for doing so. Patients who withdraw from the Surveillance should have the reason for their withdrawal recorded on the case report forms (CRF's), if at all possible. All attempts should be made to ascertain whether any patient apparently lost to follow up has actually chosen not to return or is deceased.

10 ELECTRONIC DATA CAPTURE: eCRF

All the above-mentioned pre-operative patient assessments, intra-operative details and post-operative follow-up assessments will be recorded on a CRF (Case Report Forms) which will be provided to any centre being part of the ATX Register.

The CRF will be provided electronically (secured electronic data capture:EDC). A patient blank paper case report form can be printed by surgeons wishing data collection on paper before data entry in the EDC. After EDC data entry, a hard copy can be printed as well for each patient by the surgeon(s). This EDC system (NetRegulus RM) complies with the FDA and international requirements for electronic database(s) security and performances.

The system will be secured to prevent unauthorized access to the data or to the system by using the combination of user ID and password which will be provided by Stryker SA to the authorised users of each centre. The investigator will maintain a list of individuals who are authorized to enter or correct data in the system.

The surgeon and his/her other defined users will receive system documentation, training and support for the use of the EDC. All required information collected during the following period must be entered by the investigator or designated representative in the EDC. All data entry, modification or deletion will be recorded automatically in an electronic audit trail (tracking of the data entered or modified). The combination of both user ID and password will correspond to the surgeon electronic signature which will be required for patient data validation.

The secured database will be physically hosted by Stryker Orthopaedics Mahwah, New Jersey (US).

Strict confidentiality and anonymity will be applied: only the subject number will be recorded in the database.

The investigator will maintain a personal subject identification list (subject numbers with the corresponding subject names) to enable records to be identified.

11 SURVEILLANCE MONITORING

During the course of the ATX Registry and thereafter until the centre has been closed, the monitor(s) possibly visit the Centre(s) recruiting patients into the Registry by prior arrangement. The clinical Study manager or monitor can also be contacted concerning any problems or queries regarding the clinical ATX Registry.

Clinical Study Manager Europe: [name]

[contact]

[contact]

E-Mail: [contact]

The monitor shall be given unhindered access to monitor relevant source documents (including medical records) to enable complete data verification, but with respect to the patient's integrity as described in section 17.4.

12 ANALYSIS OF RESULTS

Results obtained from the ATX Registry will be tabulated and statistically analysed by Stryker's Clinical Research Department using an appropriate statistical software package. An interim analysis of the data will be made once appropriate patients are included in the Registry.

12.1 Statistical Analysis

The main aim of the register is to document the patient's safety and survivorship of the Accolade stem and Trident/Titanium cup during the follow-up. The main failure item to be considered for Kaplan-Meier survival curves is surgical revision of the Accolade stem or Trident/Titanium cup but all other adverse events types can be separately considered as failures for Kaplan-Meier survival curve assessment.

In addition to the Kaplan Meier survival curves, the surgeons involved in the register will have the possibility to analyse the following statistical descriptions/comparisons:

- Demographic and pre-operative assessments
- Intra-operative assessments
- Post-operative pain and function assessments: Harris Hip Score
- Oxford Hip Score
- Quality of Life assessments: EQ5D
- Adverse events and device-related adverse events
- Revisions/removals

Frequency and percent distributions will be presented in tabular form for categorical variables. The mean, standard deviation, minimum and maximum values will be presented for quantitative variables.

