15.4	PERSONAL DATA PROTECTION	19
16	REFERENCES	20

APPENDICES

- I Declaration of Helsinki**
- II Patient Information Sheet and Informed Consent**
- III Investigator agreement**
- IV Accolade Component Sizes**
- V Trident Component Sizes**
- VI Tritanium Component Sizes**
- VII X3 Component Sizes**
- VIII Head Component Sizes**
- IX Accolade II Component Sizes**

THE ATX REGISTRY

ACCOLADE/ACCOLADE II STEM & TRIDENT/TRITANIUM CUP WITH X3 INSERT

INTERNATIONAL MULTICENTRE SURVEILLANCE REGISTER

PROTOCOL SUMMARY

- **Surveillance design:**

International multicentre, prospective follow-up of a consecutive series of patients.

- **Objectives:**

To verify the Accolade/Accolade II stem and Trident/Titanium cup safety during follow-up and survivorship as described by Kaplan-Meier survival curves.

To document the patient clinical outcome of the patients who are eligible for a hip arthroplasty surgery involving an Accolade/Accolade II stem and Trident/Titanium cup.

- **Regulatory status of the device:**

Name of the hip system: Accolade™ TMZF® hip stem. Accolade II stem. Trident and Titanium cup and X3-liner. All components are CE-marked and approved for sale in Europe.

- **Participating institutions:**

Each clinic need to recruit at least 20 patients and maximum 100 patients. Institutions willing to participate to the register and fulfilling the local and international applicable regulatory requirements can participate. Sufficient human and technical resources in the centre are expected to ensure optimal data collection.

- **Patients to be enrolled:**

All patients eligible for a hip arthroplasty surgery involving the Accolade or Accolade II stem and Trident or Titanium cup who have been informed about this surveillance register and who freely consent to participate will be enrolled in the register.

Patients will be enrolled prospectively.

- **Clinical evaluations:**

Adverse events/adverse events: All intra-operative and post-operative adverse events.

Standard clinical parameters, Harris Hip Score, Oxford Hip Score and EQ5D will be registered preoperatively and at each follow-up visit.

ATX-REGISTRY

INTERNATIONAL MULTICENTRE SURVEILLANCE REGISTER

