6.2 Acetabular Component

As Acetabular component either Trident or Trident Tritanium can be used.

Trident®

The Trident™ family of products provides a range of acetabular shells to help surgeons choose the right shell and bearing option for the patient in question. These include PSL or Hemispherical, HA (PureFix™ HA) or non HA coated cups and no hole, cluster hole or multi hole options.

The Trident™ Hemispherical shells are available in sizes 42mm-70mm. The Trident™ PSL shells are available in sizes 40mm-68mm. They can be used with:

- X3™ polyethylene inserts 0°, 10°, excentric, elevated rim, or constrained, in sizes 22mm-44mm (depending on type of insert), for use with either a CoCr, LFIT™ CoCr, Alumina
- Ceramic, BIOLOX *delta* Ceramic, or Orthinox™ head and Alumina inserts 0° in sizes 28mm-36mm, for use with either a Alumina Ceramic or BIOLOX *delta* Ceramic head.
Please note, in this surveillance registry ONLY X3 liner is approved!

TridentTritanium™

TridentTritanium™Acetabular System provides surgeons with a highly porous ingrowth surface.

TridentTritanium™Acetabular System hemispherical shells are manufactured from Commercially Pure Titanium. The TridentTritanium™ shells utilize the screw hole pattern and locking mechanism from the TridentAcetabular system. TridentTritanium™ Hemispherical comes as solid back shells (no holes), cluster shells and multi-hole shells.

The hemispherical shells are available in sizes 44mm-72mm to be used with X3™ polyethylene inserts 0° (in sizes 22mm-44mm), 10° (in sizes 22mm-36mm) or with elevated rim (in sizes 28mm-36mm). The inserts are provided for either a CoCr, LFIT™ CoCr, Alumina Ceramic, BIOLOX *delta* Ceramic, or Orthinox™ heads. **Please note that in this surveillance registry ONLY X3 liners are approved!**

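### Section 12.1 requires Kaplan-Meier estimates only for surgical revision, so the percentages tabulated for other adverse events will depend on length of follow-up

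*Combined protocol and SAP*

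**What the plan says.** Section 12.1 sets the main analysis: "The main failure item to be considered for Kaplan-Meier survival curves is surgical revision of the Accolade stem or Trident/Titanium cup". For everything else the wording is permissive: "all other adverse events types can be separately considered as failures for Kaplan-Meier survival curve assessment".

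The section then adds a second layer: "In addition to the Kaplan Meier survival curves, the surgeons involved in the register will have the possibility to analyse the following statistical descriptions/comparisons". The list that follows includes adverse events, device-related adverse events and revisions/removals. The presentation named for such variables is "Frequency and percent distributions will be presented in tabular form for categorical variables". No denominator, time point, number at risk or comparison group is given.

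Four other places bear on how long patients are observed:

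- The Protocol Summary describes "International multicentre, prospective follow-up of a consecutive series of patients". No accrual period is stated.
- Section 12 says "An interim analysis of the data will be made once appropriate patients are included in the Registry". No date or follow-up condition is attached.
- Section 5 sets recording points at 1, 3, 5, 7 and 10 years, but ties the length of surveillance to each institution's routine.
- Section 9 provides for withdrawal and loss to follow-up.

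On the devices, Section 6.1 describes two stems that differ in material, length and medial curvature, and Section 6.2 says "As Acetabular component either Trident or Trident Tritanium can be used". Sections 3 and 12.1 do not say whether results are shown by design or combined.

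**The concern.** Safety is part of the register's main aim, yet outside revision no safety outcome has a required analysis that uses time at risk. A percentage of patients with an event, taken when some have been followed for two years and others for eight, mixes risk with duration of observation. This has two consequences.

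- **Absolute risk.** A crude percentage from incomplete follow-up is lower than the cumulative risk at the end of the schedule. Section 14.2 benchmarks risks against rates in the literature, so an understated figure would flatter the devices even if no implants are compared with each other.
- **Contrasts between implants.** Section 12.1 lets surgeons make comparisons without naming groups. If they contrast stems or cups whose patients entered at different times, or came from centres with different routines, unequal follow-up alone produces a difference in the table.

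**Working it through.** The plan gives no event rate, power or expected follow-up, so there is no figure of its own to reproduce. All hazards, follow-up times and group sizes below are assumptions. Only the scheduled visits and the cap of 1000 patients come from the documents.

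**Step 1. Crude percentage at equal risk.** With the same constant hazard h in both groups and every patient followed for T years, crude percentage = 1 − exp(−h × T).

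| h per year | Longer T | Shorter T | Longer | Shorter |
|---|---|---|---|---|
| 0.5% | 7 | 3 | 3.4% | 1.5% |
| 1% | 8 | 4 | 7.7% | 3.9% |
| 1% | 5 | 2 | 4.9% | 2.0% |
| 1% | 7 | 3 | 6.8% | 3.0% |
| 1% | 10 | 7 | 9.5% | 6.8% |
| 1% | 10 | 10 | 9.5% | 9.5% |
| 3% | 8 | 4 | 21.3% | 11.3% |

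For example, 1 − exp(−0.08) = 7.7% and 1 − exp(−0.04) = 3.9%. The true risks are identical in every row. The gap comes only from T, and it is zero when follow-up is equal.

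**Step 2. How often this would look significant.** Take 500 patients per group (half the cap) and 7 versus 3 years. A two-sided 5% test on the crude percentages would be significant in about 29%, 51% and 80% of cases at 0.25%, 0.5% and 1% per year, with no true difference. The plan names no such test. The figures show only how convincing the artefact could look.

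**Step 3. Does a time-based summary remove it?** A simulation used 1000 runs, 500 patients per group and a hazard of 1% per year in both. Potential follow-up was uniform over 5–9 years in one group and 2–5 years in the other.

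| Summary | Longer follow-up | Shorter follow-up |
|---|---|---|
| Crude percentage | 6.8% | 3.4% |
| 3-year Kaplan-Meier failure | 2.95% | 2.97% |
| Events per 100 patient-years | 1.01 | 1.00 |

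The true 3-year risk is 1 − exp(−0.03) = 2.96%, which Kaplan-Meier recovers in both groups. The true 10-year risk is 1 − exp(−0.10) = 9.5%, so both crude figures fall short of it.

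**Step 4. Events that cluster early.** Suppose 3% of patients have an event at or soon after surgery and none have one later. The crude percentage is 3% whatever the follow-up, so no bias arises. The patient-year rate now misleads in the other direction. Per 100 patients, 3 events over about 800 patient-years is 0.38 per 100, and 3 over about 400 is 0.75 per 100. The group with shorter follow-up looks twice as bad at identical risk. Patient-year rates alone are therefore not a safe replacement.

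**The case against.** The strongest reply is that the main device outcome is already handled properly. Revision is the main Kaplan-Meier failure, and the tables are an optional supplement. Section 3 also says that adverse events and revisions are documented so that survival curves can be drawn. That stands for revision. It would be wrong to infer from the frequency-and-percent sentence that revisions are analysed only as percentages. It does not settle the matter for other adverse events, because Section 12.1, where the analysis is defined, only permits curves for them.

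A reader might also infer that the register plans to compare implants, that it pools the two stems and two cups, or that Accolade II patients entered later and so have shorter follow-up. The documents support none of these:

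- No objective or analysis contrasts stems or cups. The permitted comparisons could as well be across visits.
- Pooling would be an inference from silence. Designs that were pooled would also give no between-implant table to bias.
- Section 1 presents Accolade II as a development of the tapered wedge stem. That is design lineage, not order of enrolment. No accrual dates are given, and nothing suggests different timing for the cups.

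Finally, since no denominator is stated, percentages could be tabulated by scheduled visit, which would reduce the problem. That is possible, but the text does not say so, and numbers at risk would still be needed. The limits on size also stand: hazards and follow-up times are assumed, a constant hazard does not fit many of the events listed in Section 14.1, and the bias disappears once everyone has completed the same follow-up.

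**Conclusion.** The point holds in a limited form. Kaplan-Meier is required only for surgical revision. For other adverse events, and for the revision/removal table, the stated presentation is a crude percentage with no time reference. With varying observation time, most clearly at the undated interim analysis, that percentage understates cumulative risk.

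A distortion between implants is conditional. It arises only if surgeons contrast stems or cups and follow-up differs between them. Under an assumed common hazard of 1% per year, half the follow-up gives about half the percentage (8 versus 4 years in Step 1). The effect concerns events that accrue over years, not intra-operative or early ones. Because the main revision analysis already allows for censoring, this is a cheap improvement and not a flaw in the primary result.

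**What to change.** In Section 12.1, replace the permissive wording with a requirement:

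- Report post-operative adverse events, device-related events and revisions as Kaplan-Meier estimates at 1, 3, 5, 7 and 10 years, with confidence intervals and numbers at risk.
- Do this overall and by stem and cup type, at both interim and final analyses. This also settles how the designs are presented.
- Keep crude counts as a supplement, and keep simple percentages for intra-operative events.
- Do not rely on patient-year rates alone, since they assume a roughly constant hazard.
- Label any contrast between implants as non-randomised and descriptive.

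The data are already collected: surgery date and components (Section 7.1.2), event onset date (7.1.4), and dates of last visit and termination (7.1.5). The cost is a change of wording and slightly more programming. The downside is wide intervals in small implant subgroups and at the late time points.

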3 OBJECTIVES & METHODS

- Safety & survivorship: All adverse events / failures or revision of the Accolade stem, Accolade II stem and Trident/Titanium cup will be documented in order to draw Kaplan Meier survival curves of the Accolade stem and Trident/Titanium cup over follow-up.
- Clinical outcome: Standard clinical parameters (Harris hip score, Oxford Hip Score and EQ5D) will be obtained to allow the surgeon to assess the clinical outcome of the patient.

The register will follow the standard clinical procedures used by the institutions for patient selection for hip arthroplasty surgery, patient surgery and patient follow-up. Therefore there will be, with regard to this register, no additional assessment, examination, procedure or follow-up visits compared to those usually performed in the institution (routine standard normal procedures).

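### Section 12.1 gives the Harris, Oxford and EQ5D scores no within-patient change, confidence interval, longitudinal analysis or rule for missed visits, so 10-year visit means can mix change with who attends

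*Combined protocol and SAP*

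**What the plan says.** The protocol summary, under clinical evaluations, plans the scores before and after surgery: "Standard clinical parameters, Harris Hip Score, Oxford Hip Score and EQ5D will be registered preoperatively and at each follow-up visit". Sections 7.1.1 and 7.1.3 list all three scores at both stages, and Section 5 sets the follow-up visits at 1, 3, 5, 7 and 10 years. Section 3 gives their purpose: they "will be obtained to allow the surgeon to assess the clinical outcome of the patient".

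Section 12.1 makes safety and survivorship the main aim. Beyond the survival curves, "the surgeons involved in the register will have the possibility to analyse the following statistical descriptions/comparisons". The list that follows includes "Demographic and pre-operative assessments" and, as separate items, "Post-operative pain and function assessments: Harris Hip Score", the Oxford score and EQ5D. The one statement of method for such variables is "The mean, standard deviation, minimum and maximum values will be presented for quantitative variables".

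On attendance, Section 3 says the register brings "no additional assessment, examination, procedure or follow-up visits compared to those usually performed in the institution". Section 5 ties the length of surveillance and the visit schedule to the institution's routine. Section 9 asks centres to find out whether patients apparently lost have chosen not to return or have died, but gives no rule for the analysis.

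**The concern.** The clinical-outcome question is how patients change from before surgery and whether the gain lasts to 10 years. The data to answer it are planned for each patient. The named statistics describe a distribution at one time. They do not link a patient's later score to that patient's own starting point, and they give no interval.

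The second difficulty is who contributes. Over 10 years patients die, withdraw or are lost, and some centres may not routinely see patients at every planned visit. If those who do worse are less often seen, a row of visit means can look stable or improving when the cohort is not. The planned table gives a reader no means of telling the two apart.

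**Working it through.** **What can be reproduced.** Nothing. The documents contain no score SD, correlation, attendance rate or sample-size calculation, and the 1000 patients in Section 4.1 are a cap. Everything below is illustration on assumed inputs.

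**1. Simple size of the bias.** Bias of the attenders' mean = fraction missing × (mean score of attenders − mean score of those missing). Assumed 20-50% missing and gaps of 5-10 points:
- 0.2 × 5 = 1.0 point
- 0.3 × 10 = 3.0 points
- 0.5 × 10 = 5.0 points

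**2. Dropout that depends on the previous score (simulation).** Assumed: correlation 0.6 between post-operative visits and 0.3 with the pre-operative score; everyone seen at 1 year; permanent dropout after that; 50-70% still attending at 10 years; odds of staying 1.25 to 2.0 per SD of the previous score. Bias at 10 years:
- mean of attenders: about 0.05 to 0.23 SD too high
- paired change in attenders: about 0.025 to 0.116 SD too high
- sequential regression using all visits (equivalent here to a likelihood-based estimate): under 0.01 SD

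The last result is expected, because the assumed dropout is missing at random given the recorded scores.

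**3. A second selection model.** Let p be the attendance and ρ the correlation between the tendency to attend and the 10-year score. Bias in SD units = ρ·φ(z_p)/p, where φ is the standard normal density and z_p the normal quantile of p. For p = 0.6, φ(z_p) = 0.386 and 0.386/0.6 = 0.644:
- ρ = 0: 0
- ρ = 0.1: 0.064 SD
- ρ = 0.5: 0.322 SD

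At p = 0.8 the same range of ρ from 0.1 to 0.5 gives 0.035 to 0.175 SD.

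**4. Does change from baseline in attenders remove the bias?** Let attendance depend only on the pre-operative score (correlation g), let r be the correlation between the pre-operative and 10-year scores, and let the true change be zero. Write k = g·φ(z_p)/p. Attenders' pre-operative mean is then off by k and their 10-year mean by r·k.
- Visit mean minus everyone's pre-operative mean = r·k. Smallest case (r = 0.3, p = 0.8, g = 0.3): 0.3 × 0.105 = +0.03 SD. Largest (r = 0.5, p = 0.6, g = 0.5): 0.5 × 0.322 = +0.16 SD.
- Paired change in attenders = −(1 − r)·k. Smallest (r = 0.5, p = 0.8, g = 0.3): −0.5 × 0.105 = −0.05 SD. Largest (r = 0.3, p = 0.6, g = 0.5): −0.7 × 0.322 = about −0.22 SD.
- Estimate adjusted for baseline, using all pre-operative scores: 0.00 SD in simulation.

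Paired change in attenders is therefore not a correction for attrition. Here it is biased in the opposite direction to the visit mean.

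**5. Precision.** With complete pairs and equal SDs, SE(paired)/SE(unpaired) = √(1 − r):
- r = 0.2: 0.894
- r = 0.3: 0.837
- r = 0.4: 0.775
- r = 0.6: 0.632

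The paired SE is 11-37% smaller for r from 0.2 to 0.6, and 16% smaller at the 0.3 assumed in step 2. With complete pairs the mean change equals the difference of the two visit means, so ignoring the pairing then costs precision and not validity.

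**The case against.** The strongest reply is that Section 12.1 is unspecific rather than wrong. Its sentence on quantitative variables is general, its list allows for comparisons, and a change score is itself a quantitative variable with a mean and SD. A before-and-after comparison would fit. A reader might infer that the pre-operative scores go unused, but pre-operative assessments are an item in the list. What is absent is any specified use of them as the patient's own reference. A reader might also infer that the plan prescribes means of whoever attends each visit. That follows only from its silence. These points stand. But an analysis that surgeons have the possibility to run, with no method named, is a weak basis for a stated objective.

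Second, selective attendance is not documented. Inclusion criterion 4 requires willingness to attend, exclusion criterion 16 removes patients unlikely to comply, and Section 9 asks for losses to be followed up. A centre that omits a visit biases the mean only if its patients score differently. All of this is fair, and it makes the bias a risk and not a finding. The named statistics would still not show whether the risk had materialised.

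Third, a mixed model looks unbiased in step 2 because the dropout there was made missing at random, and a standard mixed model implicitly carries scores on beyond death. Both points stand and limit what may be claimed for the model.

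Last, this is a single-arm surveillance register with no hypothesis on the scores. That lowers the importance of the point but does not remove it.

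**Conclusion.** The point holds as a gap in the analysis of the second objective. Section 12.1 names mean, SD, minimum and maximum, and nothing in the documents specifies within-patient change, an interval, a longitudinal analysis or the handling of missed visits for the three scores. Visit means over 10 years can therefore mix change with attendance.

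The size cannot be had from the documents. It is about 0.05 to 0.23 SD under the dropout assumed in step 2, of similar order under the selection model in step 3, and zero if attendance is unrelated to score. It would be too strong to conclude that the plan must give a distorted answer even when followed exactly, since no attendance figure supports that. The main aim, safety and survivorship, is not touched. The change is worth making because the data are already planned and the cost is low.

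**What to change.** Keep the descriptive table in Section 12.1 and add, for each score and visit:

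1. The number of patients contributing and the pre-operative mean of those same patients, which shows selection on the starting score.
2. The mean within-patient change from the pre-operative value with 95% CI, described as applying to attenders and not as a correction for attrition.
3. A repeated-measures mixed model using all available visits, with the pre-operative score in the response vector, visit and stem type as fixed effects and centre as a random effect. Report the model-based change from the pre-operative value with 95% CI.

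State that item 3 is valid under missing-at-random. State how scores after revision are treated. State also whether the means refer to patients alive at the visit or to a named hypothetical, because the model will otherwise extrapolate past death without saying so.

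The cost is wording, some programming and reliance on the missing-at-random assumption. No new data, visits or patients are needed.
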